#### 5.1.3 Concomitant medication date imputation

This algorithm is used when *event* is the partial start date of the concomitant medication or non-drug therapy/procedure.

The following table explains the notation used in the logic matrix. Please note that **completely missing start dates** will not be imputed. Also note that imputation of a start date must not result in a date later than the end date. In such case, start date will be max(01-MMM-YYYY, Treatment start date) if only the day is missing and max(01-JAN-YYYY, Treatment start date) if day and month are missing.

	Day	Month	Year
Partial CMD Start Date	Not used	MON	YYYY
Treatment Start Date	Not used	TRTM	TRTY

The following matrix explains the logic behind the imputation.

	MON MISSING	MON < TRTM	MON = TRTM	MON > TRTM
YYYY MISSING	(C2) Uncertain	(C1) Uncertain	(C1) Uncertain	(C1) Uncertain
YYYY < TRTY	(D) Before Treatment Start	(A) Before Treatment Start	(A) Before Treatment Start	(A) Before Treatment Start
YYYY = TRTY	(C2) Uncertain	(A) Before Treatment Start	(C2) Uncertain	(B) After Treatment Start
YYYY > TRTY	(E) After Treatment Start	(B) After Treatment Start	(B) After Treatment Start	(B) After Treatment Start

The following table is the legend to the logic matrix.

Relationship	Date Imputation
Before Treatment Start	Partial date indicates CMD start date prior to Treatment Start Date
After Treatment Start	Partial date indicates CMD start date after Treatment Start Date
Uncertain	Partial date insufficient to determine relationship of CMD start date relative to Treatment Start Date
Imputation Calculation	
(A)	15MONYYYY
(B)	01MONYYYY
(C1 or C2)	IF relative reference start = before THEN Treatment Start Date -1 day ELSE IF relative reference start = '' THEN Treatment Start Date +1 day
(D)	01JULYYYY
(E)	01JANYYYY

Concomitant Medication End Date Imputation:

If not ongoing then

Imputed date = date part of CMENDTC, if complete date

Imputed date = min(reference end date, DEC 31) , if month is missing, (C2, D, E)

Imputed date = min(reference end date, last day of the Month) , if day is missing. (A, B, C1)

Concomitant Medication Date Flag:

If not a complete date then

Y - If year of the imputed date <> YYYY else

M - If month of the imputed date <> MON else

D

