#### **2.4.2 Prior, concomitant, and post therapies**

Medications will be identified using the WHO dictionary including ATC code and presented for the SAF. Prior medications are defined as any medications taken prior to the first administration of study drug (regardless of whether they are stopped or continued after randomization). Concomitant medications and significant non-drug therapies are defined as those used during the double-blind period. Prior and concomitant medications will be summarized by treatment group in separate tables. Medications will be presented in alphabetical order, by ATC codes and grouped by anatomical main group (the 1st level of the ATC code, e.g. “Cardiovascular system”, C), and by the first subgroup, e.g. “Lipid modifying agents” (C10). Tables will also show the overall number and percentage of subjects receiving at least one drug of a particular ATC code and at least one drug in a particular anatomical main group and first subgroup.

Concomitant medications that were prohibited as per protocol and given between start and end of treatment period as well as significant non-drug therapies, and medications that are permitted only if the dose is stable within 25 percent of the baseline dose (Table 5-4 in the protocol) will be provided in separate tables.

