### **5.1.3.1 Prior therapies date imputation**

Same as concomitant medication date imputation (as applicable).

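### The SAP's fallback for a partial medication start date yields a start after the recorded end date for every drug that reaches it and ended before first dose

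*SAP*

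**What the plan says.** SAP 5.1.3 imputes a partial start date in two steps.

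- **First pass.** A matrix compares the recorded month and year with those of treatment start. Rule A (month known, before the treatment-start month) gives the 15th of that month. Rule D (only an earlier year known) gives 1 July. Rule B (a later month) gives the first of that month, and rule E (only a later year known) gives 1 January. Rules C1 and C2 cover the uncertain cells. They give "IF relative reference start = before THEN Treatment Start Date -1 day", or one day after treatment start when the reference flag is blank.
- **Fallback.** The governing condition is that "imputation of a start date must not result in a date later than the end date". When the first pass breaks it, the instruction is: "In such case, start date will be max(01-MMM-YYYY, Treatment start date) if only the day is missing". The other branch is "max(01-JAN-YYYY, Treatment start date) if day and month are missing".

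Complete end dates are kept as recorded. For prior therapies, SAP 5.1.3.1 only refers back to this section, as far as applicable.

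These dates can feed two places:
- SAP 2.4.2 tabulates prior, concomitant and prohibited medications. For the first, "Prior medications are defined as any medications taken prior to the first administration of study drug". The prohibited table covers "Concomitant medications that were prohibited as per protocol and given between start and end of treatment period".
- SAP 5.3.5 sets the statin flag to Yes for an ATC C10 drug that was ongoing at randomization or that begins in the treatment epoch.

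**The concern.** The condition and its remedy contradict each other for drugs that ended before first dose, and those drugs make up almost all the cases in which the remedy is called. The result is an impossible record: a recorded month and year are overwritten by Day 1, and the drug starts after it stopped.

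No later step repairs this. The adverse-event rules in SAP 5.1.2 reconcile an imputed end date that falls before the start; the medication rules have no counterpart. Protocol 6.2.5 collects medications taken over the six months before enrollment, so drugs stopped before first dose can be expected in the database.

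At stake is whether the medication tables and the C10 flag describe background and on-study treatment correctly in each arm.

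**Working it through.** The plan gives no figure to reproduce; this is a check of a date rule.

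**General argument.** Let T be treatment start, E the recorded end date and x the first of the known month or year. The fallback is max(x, T) ≥ T. If E < T, then max(x, T) ≥ T > E for every x, so the condition start ≤ E always fails.

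**When the fallback is called** (known year, complete and consistent end date):
- Rule A: the drug stopped on days 1–14 of its start month. That month precedes the month of T, so E < T.
- Rule D: the drug stopped in January–June of its start year. That year precedes the year of T, so E < T.
- Rule C2: the first pass is T−1 or T+1. It exceeds E if the drug stopped earlier than that in the same month (month known) or the same year (month missing) as T. The only case with E ≥ T is E = T with a blank flag. The fallback then gives T, which is correct.
- Rules B and E give the first day of the month or year, so they cannot exceed a consistent end date.

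**Worked cases, assuming T = 20 June 2019.**

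| Recorded start | Recorded end | First pass | Fallback | Days after end |
|---|---|---|---|---|
| Mar 2019 | 10 Mar 2019 | 15 Mar 2019 (A) | 20 Jun 2019 | 102 |
| 2019, flag blank | 15 Feb 2019 | 21 Jun 2019 (C2) | 20 Jun 2019 | 125 |
| Jun 2019, flag 'before' | 10 Jun 2019 | 19 Jun 2019 (C2) | 20 Jun 2019 | 10 |
| Jun 2019, flag blank | 20 Jun 2019 | 21 Jun 2019 (C2) | 20 Jun 2019 | 0 (works) |

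In the first and third rows the fallback is even later than the date it replaces.

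**Enumeration.** The same T was run against 900 daily end dates from 1 January 2018, all partial starts in 2018–2020 not after the end date, and both flag values.
- E < T, flag blank: 238 (A) + 181 (D) + 170 (C2, month missing) + 19 (C2, month known) = 608 calls.
- E < T, flag 'before': 238 + 181 + 169 + 18 = 606 calls.
- Total 608 + 606 = 1214 calls; the start was after the end in 1214 of 1214.
- E ≥ T: 2 calls, both with E = T; both are correct.

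**Restricted to what the protocol collects.** Screening lasts at most 10 weeks (Protocol 3.1) and medications are captured for six months before enrollment (Protocol 6.2.5). For this T, consent is no earlier than 11 April 2019, so capture reaches back to about 11 October 2018.
- Rule A: 4 days in October + 7 months × 14 days = 102 per flag value.
- Rule D: none, because its end dates fall in January–June 2018.
- Rule C2: unchanged.
- Total (102 + 170 + 19) + (102 + 169 + 18) = 291 + 289 = 580 calls; 580 of 580 fail.

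Rule D can matter only when first dose falls early in the year. With first dose on 15 January 2019, capture reaches back to about 6 May 2018. A drug recorded as started in 2018 and stopped on 20 June 2018 is then given a start of 15 January 2019, 209 days after it stopped.

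These counts are calendar combinations that show the logic. They do not estimate how many patients or records are affected.

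**Year missing.** Rules C1 and C2 still give T−1 or T+1, but the fallback has no year to work with and is undefined.

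**The case against.** Several stronger readings are tempting, and the documents do not support them.

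- **That all drugs stopped before the trial are moved to Day 1.** They are not. Complete start dates never reach the fallback, and neither do partial ones whose first imputation is on or before the end date.
- **That the SAP 2.4.2 tables will be wrong.** A reader might infer this from the false start, but those definitions rest on when a drug was taken or used, not on the imputed start. End dates are kept, so a program that checks them could file the drug correctly as prior. The SAP gives no record-level derivation, so misclassification is possible, not shown. The same holds for apparent prohibited use or an apparent new start of a stable-dose drug from Protocol Table 5-4.
- **That the enumeration shows a high error rate.** More than half of the 1214 combinations (1214 − 580 = 634) lie outside the capture window for the assumed first dose, and none is weighted by how often it occurs.
- **That the main results are affected.** The primary safety summaries and the histology analyses are not shown to use these dates, and the rule is identical in every arm.

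The C10 flag is also limited. A patient's value changes only if no other C10 drug was ongoing at randomization or begun on treatment, and no unredacted analysis uses the flag.

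All of this narrows the consequence. None of it removes the contradiction, which follows from two adjoining sentences of the SAP.

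**Conclusion.** The point holds in limited form. For every drug with a partial start date that reaches the fallback and ended before first dose, SAP 5.1.3 produces a start after the end date, against its own condition. The one situation in which the fallback works is an end date equal to first dose with a blank reference flag.

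One consequence follows directly from the text. A C10 drug stopped before the trial would meet the treatment-epoch branch of SAP 5.3.5, which has no end-date check, because the treatment period defined in SAP 2.1 includes the Baseline visit. Misclassification in the SAP 2.4.2 tables depends on programming that the SAP does not specify.

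The conclusion assumes a literal reading of the rule, a known start year, and complete end dates consistent with the recorded start. The number of affected records cannot be derived from the documents. The impact is confined to descriptive medication tables and one derived flag, but the error is certain where the rule applies and cheap to remove.

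**What to change.** In SAP 5.1.3, and so in 5.1.3.1, replace the fallback as follows, to apply when the first-pass start is later than the end date:

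1. **End date before treatment start.** Set the start to 01-MON-YYYY if only the day is missing, or to 01-JAN-YYYY if day and month are missing, with no maximum against treatment start. Classify the drug as prior only.
2. **End date on or after treatment start.** Keep the current maximum. Dropping it everywhere would break the case that works: a drug ending on the first-dose day and not flagged as started before would be given an earlier start and look prior.
3. **Year missing and end date before treatment start.** Leave the start unimputed; the end date alone makes the drug prior.

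In the enumeration, the first of the month or year gave a start after the end date in 0 of the 1214 failing combinations, and keeping the maximum left the 2 working ones unchanged. The corrected start also keeps these drugs out of the treatment-epoch branch in SAP 5.3.5.

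The cost is a line or two of SAP text and the matching derivation code, ideally before database lock. No new data are needed.

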### **5.1.3.1 Prior therapies date imputation**

Same as concomitant medication date imputation (as applicable).

### **5.1.3.2 Post therapies date imputation**

Not applicable.

### **5.1.4 Other imputations**

A multiple imputation approach will be applied to missing follow-up biopsies.

For subjects who do not have a Week 48 liver biopsy or not remain on their randomized study treatment for at least 24 weeks (even if a Week 48 biopsy was obtained), the biopsy based outcomes will be imputed by multiple imputation (MI). It is assumed that biopsy results are missing at random (MAR). Available results for subjects who discontinue treatment before 24 weeks are set to missing for this analysis. Imputation will be based on available results from subjects who did not discontinue study treatment, thus addressing the question what the results would have been if subjects had not discontinued. The imputation model will take into account the treatment group, the baseline fibrosis stage (categorical), [REDACTED], the baseline ALT, [REDACTED] and change in ALT, [REDACTED] from baseline to Week 12 and to Week 24 (continuous). As there is only one post-baseline biopsy assessment, an arbitrary missing pattern is assumed and a fully conditional specification (FCS) method with logistic regression is applied. The randomization seed is 4572201 and the number of imputations will be set to 50.

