6.2.6 Liver evaluation

6.2.6.1 Liver biopsy

[figure not shown]
Patients must have histologic evidence of NASH and liver fibrosis stage 2 or 3 (NASH clinical research network (CRN) staging criteria) demonstrated on liver biopsy during the Screening period. Alternatively, a historical biopsy can be used if performed within 6 months prior to screening, if:

- the patient has been receiving any of the therapies listed in [Table 5-4](#), the dose must have been stable (since 1 month before the biopsy up to and including screening),
- the patient weight has been stable (maximum weight loss of 10% since biopsy up to and including screening).

Five to eight Baseline Biopsy slides, unstained and prepared from biopsies performed during the screening period or \leq 6 months prior to the screening visit, will be sent to a Central Reader to determine eligibility. Patients will be treated for 48 weeks and an end of treatment biopsy will be performed and slides submitted to the Central Reader. A manual detailing all the requirements will be supplied to each study site.

For the patients who do not have an historical liver biopsy, [REDACTED] may be a useful pre-screening tool prior to liver biopsy for cases of indeterminate clinical NASH (F2/F3) diagnosis.

In case of premature treatment discontinuation, the end of treatment biopsy should only be performed if the patient has received at least 24 weeks of study treatment.

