9.5 Analysis of secondary variables

9.5.1 Efficacy variables

An overview of the secondary efficacy variables and planned analysis is given in [Table 9-2](#).

Table 9-2 Secondary efficacy variables and analyses

Variable	Analysis
At least a one point improvement of fibrosis	Cochran-Mantel-Haenszel test controlling for baseline fibrosis stage for each tropifexor + CVC combination vs. each monotherapy treatment, with supporting information from risk differences, odds ratios with 95% confidence intervals
Resolution of steatohepatitis (as determined by central pathologist)	Cochran-Mantel-Haenszel controlling for baseline fibrosis stage for each tropifexor + CVC combination vs. each monotherapy treatment, with supporting information from risk differences, odds ratios with 95% confidence intervals

There is a single secondary objective in this study which is to characterize the efficacy of tropifexor + CVC in patients with NASH with fibrosis stage F2/F3 as assessed by histological improvement after 48 weeks of treatment compared to monotherapies (tropifexor and CVC) relative to baseline biopsy. There are two estimands that will be used to evaluate this objective.

The first estimand is the difference on the proportion of patients on the different tropifexor + CVC regimens who achieve at least a one point improvement in fibrosis at Week 48 compared to tropifexor and CVC monotherapy patients. It is assumed that anyone who does not have a Week 48 liver biopsy or does not remain on their randomized study treatment for at least 24 weeks (even if a Week 48 biopsy was obtained) will have their outcome imputed by multiple imputation (MI). For subjects who remain on their randomized study treatment for at least 24 weeks, but discontinue study treatment prior to Week 48, available Week 48 biopsy results will be used as observed. This is a hypothetical strategy addressing the question “what would be the outcome if subjects had stayed at least 24 weeks on treatment and a Week 48 biopsy had been obtained”. Treatment differences between tropifexor + CVC combination therapy and monotherapy with tropifexor or CVC will be evaluated using a Cochran-Mantel-Haenszel test controlling for baseline fibrosis stage (F2/F3). The estimand will be evaluated in the FAS population.

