### **2.7.3 Handling of missing values/censoring/discontinuations**

Missing baseline data (if applicable) for the secondary endpoints will not be imputed.

Missing follow-up data for the secondary endpoints will be handled as follows:

If a patient stayed on randomized study treatment for less than 24 weeks, missing data will not be imputed, and if data are available (which is not expected as per protocol) they will not be included in the analysis.

If a patient stayed on randomized study treatment for at least 24 weeks, but follow-up data are not available, data will be imputed by multiple imputation (see Section 5.1.4).

[figure not shown]
If a patient stayed on randomized study treatment for at least 24 weeks, and follow-up data are available, data will be used as observed, even if treatment was discontinued prior to Week 48.

Due to the COVID-19 pandemic, it was not possible for some patients to return in time for the Week-48 visit to perform a liver biopsy. Instead, it was possible for additional treatment to be dispensed (see drug dispensing plan in Section 5.5.2 in the protocol), and the Week-48 liver biopsy could be delayed up to approximately 12 weeks. Since the purpose of the secondary efficacy analysis is to evaluate the potential histological benefit of study treatment, all biopsies obtained, including those from eligible patients after Week 48, will be included in the analysis as Week-48 biopsies.

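### Both histology endpoints rely on missing-at-random imputation that no readable analysis varies, and the SAP contradicts itself on whether patients with under 24 weeks of treatment are imputed at all

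*SAP*

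**What the plan says.** Three passages govern patients whose Week 48 histology is missing or not used.

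- **Protocol 9.5.1** uses multiple imputation for anyone without a Week 48 biopsy or with less than 24 weeks on randomized treatment. It names the approach: "This is a hypothetical strategy addressing the question" of "what would be the outcome if subjects had stayed at least 24 weeks on treatment and a Week 48 biopsy had been obtained".
- **SAP 5.1.4** imputes the same two groups and sets to missing any biopsy from a patient who stopped before 24 weeks. It states "It is assumed that biopsy results are missing at random (MAR") and "Imputation will be based on available results from subjects who did not discontinue study treatment". On covariates: "The imputation model will take into account the treatment group, the baseline fibrosis stage (categorical"), followed by baseline ALT, ALT change to Weeks 12 and 24, and some redacted terms.
- **SAP 2.7.3** says otherwise for the under-24-week group: "If a patient stayed on randomized study treatment for less than 24 weeks, missing data will not be imputed", and any data they do have are left out. Patients with at least 24 weeks but no biopsy are imputed. For those with at least 24 weeks and a biopsy, "data will be used as observed, even if treatment was discontinued prior to Week 48".

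Protocol 6.2.6.1 adds that, after premature discontinuation, "the end of treatment biopsy should only be performed if the patient has received at least 24 weeks of study treatment". Histology for earlier stoppers is therefore absent by design.

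The readable supportive analyses (SAP 2.7.4 and section 4) cover extended treatment, 10% weight loss, modified Ishak staging, real-time reading, qualitative paired comparisons and a NAS-based definition of resolution. The protocol's sensitivity analyses address biopsies delayed by COVID-19.

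**The concern.** Stopping is unlikely to be unrelated to outcome. Protocol 5.6.2 lists liver-test elevations, drug-related serious events and patient wish among the reasons for stopping. Protocol 1.1 says that both drugs may raise transaminases, possibly additively. More early losses in a combination arm are therefore plausible.

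If they occur, multiple imputation fills those patients in from patients who stayed on drug, and the exclusion rule in SAP 2.7.3 drops them. Neither rule makes the arm's response rate fall because patients could not stay on treatment. The trial is meant to inform whether the combination is developed further (protocol 1.2), and its primary question is safety and tolerability. A reader will want to know how far the histology result depends on an assumption that these data cannot test. No readable analysis shows that, and the SAP does not settle which patients the assumption covers.

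**Working it through.** **1. The rules side by side**

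| Patient | Protocol 9.5.1 | SAP 5.1.4 | SAP 2.7.3 |
|---|---|---|---|
| Under 24 weeks on treatment, with or without biopsy | Imputed | Imputed | Not imputed, left out |
| At least 24 weeks, no biopsy | Imputed | Imputed | Imputed |
| At least 24 weeks, biopsy available | As observed | Not imputed | As observed |

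The conflict is confined to the first row. SAP 5.6 refers to imputing eligible patients without defining eligible, so it does not resolve it.

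**2. The plan's own power figures**

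Inputs from protocol 9.8.2 and SAP 3.2: combination 69%, tropifexor 42%, CVC 35%, 50 per arm, two-sided alpha 0.10, continuity-corrected chi-square test.

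With d the difference, the effective size m solves n = (m/4)[1 + √(1 + 4/(m·d))]². Then power = Φ{[d − 1.645·√(2p̄(1−p̄)/m)] / √([p₁(1−p₁) + p₂(1−p₂)]/m)}.

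For 69% vs 42%: m = 42.87, numerator 0.270 − 0.1766 = 0.0934, denominator 0.1033, z = 0.904, power 81.7% (stated 81%). For 69% vs 35%: 95.1% (stated 95%). Both reproduce.

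**3. Illustration with assumed missing shares**

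Amendment 3 gives 193 randomized, and 193/4 ≈ 48 per arm. With complete data, 69% vs 42% at 48 per arm gives 80.0% power.

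- *Missing at random.* The expected difference is 69 − 42 = 27 points at any missing share. Power is approximated from available cases. For 20% and 10% missing, 48 × 0.8 = 38.4 and 48 × 0.9 = 43.2, with harmonic mean 2 × 38.4 × 43.2/81.6 = 40.7. For 10% in both arms, n = 43.2.
- *Missing as non-response.* Rate = on-drug rate × (1 − missing share), with n = 48.

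| Missing, combination / tropifexor | MAR difference | Power, available-case | Non-response difference | Power |
|---|---|---|---|---|
| 20% / 10% | 27 points | about 73% | 55.2 − 37.8 = 17.4 points | 44% |
| 10% / 10% | 27 points | about 75% | 62.1 − 37.8 = 24.3 points | 71% |

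With tropifexor at 10% missing, the non-response difference is 48.3 − 37.8 = 10.5 points at 30% missing in the combination arm, and 41.4 − 37.8 = 3.6 points at 40%.

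**4. A departure that keeps the hypothetical question**

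If the missing patients in one arm respond at a rate lower by δ, the difference moves by missing share × δ. If missing combination patients respond at the tropifexor rate, δ = 69 − 42 = 27 points. At 20% missing the shift is 0.20 × 27 = 5.4 points, so the difference is 21.6. At 10% it is 24.3, and at 40% it is 16.2.

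**5. Simulation check**

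This used 50 per arm, a simplified imputation model with arm and fibrosis stage only, and missingness independent of outcome. With 20% and 10% missing, imputation gave 26.6 points and non-response 17.0. With true rates of 42% in both arms and 30% and 10% missing, imputation gave 0.1 points and non-response −8.3. Missing at random holds here by construction. The runs show what each method estimates, not whether the assumption is true in this trial.

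**The case against.** The strongest reply is that the protocol declares a hypothetical strategy, and imputation under missing at random is the natural estimator for it. Non-responder imputation answers a composite question, so most of the move from 27 to 17 points is a change of question, not bias. That stands, and it is why the planned analysis should remain the main one.

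A reader might infer three stronger things that the documents do not support.

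- *That everyone who stops early keeps the arm's full response rate.* Patients with at least 24 weeks on drug and a biopsy count as observed. For the others the statement is only approximate under imputation, because the model conditions on ALT and ALT change. The protection from those terms may be limited: after stopping, the protocol requires only the discontinuation or end-of-treatment visit and the end-of-study visit (5.6.2 and section 6), so on-drug Week 24 ALT will generally be lacking for patients who stop before then.
- *That the assumption favours the worse-tolerated arm.* This is not shown. With equal true rates and unequal losses, the simulation found no spurious advantage.
- *That power falls from 80% to 44%.* The 80% assumes complete data. The planned analysis also loses information, and the like-for-like figure is about 73%.

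Two further points limit the weight. Histology is a secondary objective, there are no pre-specified hypotheses, and sample size rests on feasibility, so the powers are illustrative. Tolerability is also reported directly, through adverse events leading to discontinuation and through discontinuation reasons by arm (SAP 2.3). Finally, parts of the SAP and of the imputation model are redacted, and the NAS-based analysis named in SAP section 4 does not appear in the readable text of 2.7.4. Absence can be judged only on what is readable.

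**Conclusion.** The point holds in a limited form. SAP 2.7.3 contradicts SAP 5.1.4 and protocol 9.5.1 on patients with under 24 weeks of treatment. Separately, all imputation of the histology endpoints is under missing at random, and no readable analysis departs from it. Under either handling, losses before Week 24 do not directly lower an arm's estimated response rate.

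The size depends on missing shares that the documents do not give. The one related figure, 6.3% stopping for adverse events after one year of CVC in the earlier phase 2b study (protocol 1.1), is only a partial guide. At 10% missing in both arms the two approaches are close: 27 against 24 points, and about 75% against 71% power. At 20% and 10% they part: 27 against 17 points, and about 73% against 44%. These figures assume the planning rates of 69% and 42%, 48 per arm, and an available-case approximation to the planned stratified analysis.

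This is a cheap improvement to what the trial can say about histology. It is not evidence that the main analysis is biased.

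**What to change.** 1. Reconcile SAP 2.7.3 with SAP 5.1.4 and protocol 9.5.1, so that one rule covers patients with under 24 weeks on treatment. Do this first, because it fixes which patients the added analyses apply to.
2. Keep the missing-at-random analysis under the hypothetical strategy as the main analysis.
3. Add to SAP 2.7.4, for both endpoints on the FAS:
   - a delta-adjusted (tipping-point) imputation as the sensitivity analysis, with the shift varied separately by arm;
   - a non-responder analysis, labelled as a supplementary composite estimand so that it is not read as a correction of the main result.
4. Report by arm the number of patients imputed and the reason. SAP 2.3 already gives discontinuation reasons by arm, but not the number imputed.

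The cost is a little programming on top of the existing imputation code, with no new data. The non-responder result will usually look less favourable than the main one.
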